10.1.5 Exploratory Endpoints (Cohort 1)

We will descriptively evaluate patient reported HRQOL regarding bowel, bladder and vaginal symptoms using the validated instrument, EORTC QLQ- EN 24. We will report means, standard deviations, ranges and 95% confidence interval for "Sexual/vaginal problems", "Gastrointestinal symptoms", and "Urological symptoms" symptom scales. All these outcomes will be reported separately for each treatment arm. Doses to organs at risk (including bladder, rectum, sigmoid colon, and urethra) and prescribed target in the two arms of the trial will be analyzed using descriptive statistics such as mean, standard deviation and 95% confidence interval. Comparisons between arms will use exploratory t-tests or non-parametric Wilcoxon tests as appropriate.

Exploratory endpoints will also include CTCAE v5.0 toxicities and patterns of recurrence in the two arms. Recurrences in the two arms will be tabulated as vaginal, pelvic, or distant. We will report counts, proportions, and exact 95% confidence intervals for adverse events. Kaplan-Meier curves and associated confidence intervals will be used to analyze time to recurrence.

The mean, median, standard deviation and interquartile range of total distance traveled will be reported for each study arm. A Wilcoxon rank-sum test will be used to compare the total distance traveled between the arms.

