4 STUDY DESIGN

4.1 Description:

This is a phase III, un-blinded, randomized trial comparing an experimental arm and a control arm of vaginal cuff brachytherapy: The experimental arm will treat subjects with 2 fractions of vaginal brachytherapy. The control arm will treat subjects with standard of care vaginal cuff brachytherapy of 3-5 fractions. See schema below: Patients will be randomized 1:1 to the different treatment arms.

4.2 Enrollment and data analysis for Cohort 1 has been completed. Cohort 2 will mirror the design of Cohort 1, but include additional outcome measures.

4.3 Number of Patients:

108 total patients were enrolled in Cohort 1 (54 to each study arm). An additional 80 patients will be enrolled in Cohort 2.

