6 TREATMENT PLAN

6.1 Administration Schedule

Experimental arm: 11Gy will be prescribed to the surface with a minimal treatment length of 3 cm. Two fractions will be given, one week apart. For this instance a week apart indicates an intervening weekend between treatments. Ideally treatments would be 7 days apart. Inspection of the vaginal cuff is required to ensure there is no dehiscence. Dose should be optimized to the cylinder as seen in Figure 1, Appendix D, with dose normalized to 100% at the tip and at the midpoint of the active length. Dose at $\frac{1}{2}$ cm will be recorded also. In cases of fulminant LSVI, the entire vagina may be treated per physician discretion. In most scenarios, the maximal treatment length should not exceed 5 cm. CT simulation shall be performed.

Control arm: One of the following fractions schemes are permitted based on the decision of the treating physician:

- 7 Gy at $\frac{1}{2}$ cm x 3 fractions over no more than three weeks.
- 5-5.5 Gy at $\frac{1}{2}$ cm x 4 fractions over no more than three weeks.
- 6 Gy at the surface of the cylinder x 5 fractions over no more than three weeks.

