8 STUDY CALENDAR

Examination	Screening ¹	Brachytherapy	Follow-up ⁶	Follow-up ⁶	Follow-up ⁶	Long term Follow-up ⁶
			1 month +/- 12 weeks	6 months +/- 12 weeks	12 months +/- 12 weeks	24 and 36 months +/- 12 weeks
Informed consent	X					
Medical history	X					
Eligibility criteria	X					
Vital signs	X		X	X	X	
Physical examination	X		X	X	X	
Pelvic exams	X		X	X	X	
WHO/ECOG performance status	X		X	X	X	
QLQ30 Questionnaire²		X	X	X	X	
EN24 Questionnaire²		X	X	X	X	
Collection of Cost Data⁴				X		
Collection of Distance Data⁷					X⁸	
Vaginal Cuff Brachytherapy³		X				
Adverse Event assessments		X	X	X	X	
Chart Review⁵						X
COHORT 2 Only						
COST-FACIT¹⁰			X			
Health Care Expense Survey¹¹		X	X			
NCI Diet History Questionnaire III (DHQ-3)⁹			X			
Physical Activity Questionnaire (ACT24)⁹			X			

1. All Pre-study/Screening procedures should be completed less than or equal to 12 weeks before study treatment.

2. Both the QLQ30 and EN24 questionnaires (appendix E and F) should be administered at baseline (prior to the first brachytherapy fraction) and at the 1 month, 6 month, and 12 month follow-up visits. See section 7.2.1 for guidance on participants experiencing severe emotional distress.
3. Subjects randomized to the control arm will undergo one of the three treatment options described in section 5 over no more than 3 weeks. Subjects randomized to the experimental arm will undergo the treatment described in section 5 over no more than 2 weeks. See Appendix D for treatment planning and dose reporting form.
4. Collection of cost data for analysis is described in section 9.2
5. The PI will continue to review patient medical charts at 24 and 36 months for disease reoccurrence at one of the following locations: vaginal, pelvic, or distant.
6. In person visits are preferred to allow for exams, so almost all visits will be done on site. If a patient is ill or cannot travel, questionnaires and history may be obtained via telemedicine. Missed exams will be considered deviations.
7. Patient's zip code and the location of the treatment facility will be collected and documented by the study staff.
8. If the information is not collected at the 12 month follow up visit, it will be collected at a subsequent time point or from patient's medical record.
9. Completion of the DHQ-3 and ACT24 is strongly encouraged, however, incompleteness will not result in a protocol deviation.

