9.3 Exploratory objectives

Evaluate CTCAE v5.0 toxicities

Routine safety and tolerability will be evaluated from the results of reported signs and symptoms, scheduled physical examinations, vital sign measurements, and clinical laboratory test results.

Evaluate and compare doses to organs at risk

Doses to organs at risk including bladder, rectum, sigmoid colon, and urethra, and target in the two trial arms will be evaluated from CT data sets without contours that will be sent to HCI in an anonymized fashion and compared to each other. Artificial intelligence approaches to aid in contouring will be considered. Additionally, the dose to prescribed target in each group will be calculated.

Compare total distance traveled to the cancer center for study related visits.

Total distance traveled, calculated by multiplying number of study visits by twice the distance to the cancer center. The distance to the cancer center will be calculated as the distance from the patient's zip code and the cancer center zip code.

Physical Examination

Complete and symptom-directed physical examinations will be performed by a licensed physician (or physician's assistant or nurse practitioner).

Vital Signs

Vital signs (blood pressure, respiratory rate, pulse rate and temperature) will be obtained.

Compare local recurrence and document patterns of recurrence

Local recurrence will be assessed by pelvic exam. Time points for evaluation include screening, one, six, and twelve months via study visits, and via chart review at twenty-four, and thirty-six months post treatment. Imaging may be used at the physician's discretion depending on the subject's symptoms. Recurrences in the 2 arms will be assessed according to site: vaginal, pelvic, or distant.

Report vaginal, bowel, and bladder symptoms on HRQOL using the EORTC EN24 the two treatment arms.

In addition to the QLQ C-30 core questionnaire, the EORTC module for endometrial cancer EN24 will be used to descriptively report values for the following symptom scores; "Sexual/vaginal problems," "Gastrointestinal symptoms," and "Urological symptoms." Additional questions regarding sexual symptoms and distress will also be reported.

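### The Wilcoxon comparison of total distance traveled ignores home distance, so it can be imprecise; add an estimate adjusted for one-way distance

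*Combined protocol and SAP*

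**What the plan says.** Section 9.3 (and objective 1.3.5) defines the endpoint: "Total distance traveled, calculated by multiplying number of study visits by twice the distance to the cancer center". The one-way distance is a zip-code figure: "The distance to the cancer center will be calculated as the distance from the patient's zip code and the cancer center zip code". Footnote 7 of the study calendar has staff record the patient's zip code and the treatment facility's location.

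Section 10.1.5 reports the mean, median, standard deviation and interquartile range of total distance by arm. It then states: "A Wilcoxon rank-sum test will be used to compare the total distance traveled between the arms". It plans no covariate, no comparison of visit counts, and no between-arm estimate with a confidence interval.

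The treatment contrast is set by the schedule. In the experimental arm (section 6.1), "Two fractions will be given, one week apart". For the control arm, section 4.1 says: "The control arm will treat subjects with standard of care vaginal cuff brachytherapy of 3-5 fractions". The other visits are the same in both arms; section 9.3 says: "Time points for evaluation include screening, one, six, and twelve months via study visits". The 24- and 36-month contacts are chart reviews and need no trip.

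**The concern.** Total distance is a product of two parts. Where the patient lives is known at entry and cannot be affected by treatment. The number of trips is the only part that treatment can change. An unadjusted rank test treats all the variation in residence as noise, although the plan already holds the figure that would remove it.

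Travel is part of the argument for a shorter course: sections 3.2 and 3.3 cite rural and frontier patients and long journeys for care. A non-significant Wilcoxon p-value with no accompanying estimate could be reported as no difference in travel, when control patients make one to three more treatment trips by design. The test would then have said more about the scatter of home addresses than about the schedules.

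**Working it through.** **The plan's own figure.** No effect size, spread or power is given for distance. The 54 per arm comes from the quality-of-life endpoint (section 10.1.6: SD 22.2, margin 15, one-sided 0.025, 90% power). That figure reproduces: 2 × (1.960 + 1.282)² × 22.2² / 15² = 46.0, so 47 per arm and 94 in total against 96 stated. The t-test power at 48 per arm is 90.6%.

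**Inputs from the documents.** Fractions: 2 against 3, 4 or 5. Common visits: screening plus 1, 6 and 12 months, so 4. Patients: 54 per arm (section 4.3).

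**Assumptions, because the documents are silent.** Log-normal one-way distance with log-SD 0.3 to 1.5; the mix of control schedules; in the main simulation, 90% attendance at the three follow-ups; two-sided 0.05.

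**Size of the signal.** With full attendance the visits are 6 against 7, 8 or 9. On the log scale the differences are log(7/6) = 0.154, log(8/6) = 0.288 and log(9/6) = 0.405.

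**Size of the noise.** Since log(total) = log(2 × visits) + log(one-way distance), the chance difference between arms in mean log distance has standard error SD × √(2/54). This is 0.096, 0.192 and 0.289 at log-SD 0.5, 1.0 and 1.5. At log-SD 1.0 the noise exceeds the whole 7-against-6 signal (0.192 against 0.154).

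**Hand approximation for 8 against 6 visits.** Taking the Wilcoxon efficiency as 0.955, power ≈ Φ(0.288/SD × √(54 × 0.955/2) − 1.96) = Φ(1.461/SD − 1.96).

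| Assumed log-SD | Hand approximation | Simulated power, equal 3/4/5 mix, 90% attendance |
|---|---|---|
| 0.3 | >99% | >99% |
| 0.5 | 83% | 84% |
| 0.6 | 68% | 68% |
| 1.0 | 31% | 32% |
| 1.5 | 16% | 16% |

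**Sensitivity to the control mix** (full attendance, 4 common visits):

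| Log-SD | All 3 fractions | Equal mix | All 5 fractions |
|---|---|---|---|
| 0.5 | 34% | 81% | 98% |
| 0.8 | 15% | 42% | 70% |
| 1.0 | 12% | 30% | 52% |
| 1.5 | 8% | 16% | 27% |

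**What adjustment gains.** If visit count is unrelated to home distance within arm, the expected total given arm and distance is 2 × (mean visits in that arm) × distance. This is a straight line whose slope differs by arm. Regressing total distance on arm, centred one-way distance and their interaction therefore has the right form. The arm coefficient is the distance saved at the mean home distance: for 6 against 8 visits, 2 × 2 = 4 times the mean one-way distance. Residual spread grows with distance, so robust standard errors are needed. Under the assumptions of the first table, this model's standard error is about 2.7 to 8 times smaller than that of the unadjusted difference in means, and its power is 98% to 100%.

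**Remote visits.** At log-SD 1.0, equal mix and 4 common visits, if 10% of follow-ups are remote the Wilcoxon power is 28% with them counted as trips and 31% with them excluded. At 30% remote it is 30% and 37%.

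**The case against.** - **The spread is assumed.** This stands. The documents give no distribution of distance, site mix or control-schedule mix. With narrow spread, or with mostly 5-fraction controls and moderate spread, the planned test does well. A reader might infer that residence necessarily overwhelms the visit saving; the documents do not support that as a general statement.
- **The test is valid.** This stands. Randomisation balances residence in expectation, so there is no bias. The endpoint is exploratory, was never powered, and no trial conclusion rests on it.
- **Adjustment is close to a tautology.** This stands in part. On the log scale, total distance adjusted for one-way distance gives the same arm coefficient as visit counts, and two fractions mean fewer visits by design. A log model also fails for a patient who shares the center's zip code and has distance zero. The raw-scale regression meets both problems: it keeps the absolute distance saved, which is what the objective asks about, and it accepts zeros.
- **Telemedicine.** Footnote 6 says: "If a patient is ill or cannot travel, questionnaires and history may be obtained via telemedicine". A reader might infer that the formula counts such visits as trips and so distorts the comparison. No section says that they count; the rule is unstated. The same footnote expects few of them: "In person visits are preferred to allow for exams, so almost all visits will be done on site". Brachytherapy itself cannot be remote, the follow-up schedule is common to both arms, and the effect on power is small.
- **Cohort 2.** No distance test is planned there. Distance is not among its objectives, and section 10.2.5 rules out formal testing of exploratory data.

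**Conclusion.** The point holds as one of precision on an exploratory endpoint. The unadjusted Wilcoxon test leaves a known pre-randomisation multiplier in the error. Its power at 54 per arm runs from over 99% down to 16% across assumed log-SDs of 0.3 to 1.5 with an equal control mix, and down to 8% if every control patient has 3 fractions and the log-SD is 1.5. These figures rest on a log-normal home distance and on visit patterns that the documents do not give. Neither bias nor an invalid test is shown, and remote visits are not the source of the imprecision. Section 4.2 says Cohort 1 analysis is complete, so any change there is supplementary. Severity is low.

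**What to change.** In section 10.1.5, keep the descriptive statistics and the Wilcoxon test, and add:

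1. The absolute distance saved with a 95% confidence interval, from a linear regression of total distance on arm, centred one-way distance and their interaction, with robust standard errors.
2. The ratio of visit counts between arms, with a 95% confidence interval.
3. A label stating that both are supplementary and post hoc for Cohort 1.

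If distance is reported for Cohort 2, give the same estimates with confidence intervals and no test. As a minor clarification, state in section 9.3 that remote visits are not counted as trips.

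The cost is a few lines of analysis on data already planned for collection (zip codes and visits). Two limits should be stated with the result: the visit-count part largely reflects the difference in fractions fixed by design, and the distance saved applies to the home distances of the patients enrolled.

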10.1.6 Sample Size Evaluation

We base the sample size on the precision of estimation of the Global Heath Status from QLQ-C30. The hypothesis to be tested is that the mean Global Health Status will be the same or higher one month after treatment in the Experimental Arm compared to the Control Arm. The EORTC QLQ-C30 reference values manual gives the means and SD of the Global Health Status in genitourinary cancer patients as 62.6 ± 22.2 points. We assume a standard deviation of 22.2 points for power calculations. Additional assumptions are 1:1 randomization to one of two groups, a true difference of 0 points, a Gaussian response variable, a non-inferiority margin of 15 points, alpha = 0.025 (one sided), and the use of a two sample *t*-test for the primary analysis. A non-inferiority margin of 15 points was chosen for this trial based on a combination of scientific and practical considerations. In a survey of 30 clinical trials, the definition of a clinical meaningful change in quality of life questionnaire data varies widely, with margins up to 10-15 point required for clinical significance (Cocks KT, et al 2008). With these assumptions a total evaluable sample size of 96 will provide 90% power. The planned sample size of 108 randomized equally to two arms allows for a dropout rate of approximately 10%.

10.2 COHORT 2

10.2.1 Sample Size Determination

The primary endpoint for Cohort 2 is the Functional Assessment of Chronic Illness Therapy (FACIT)-COST score. A preliminary estimate of the mean COST score in each arm will be reported for cohort 2, along with a 95% Gaussian confidence interval. The published standard deviation for FACIT-COST is approximately 12.³⁶ With the planned sample size of N = 40 subjects per arm, and assuming a standard deviation of approximately 12, a 95% confidence interval for mean COST will have a width of approximately 7.6 points.

10.2.2 Population for Analyses

All subjects who have received one dose of radiation and have completed at least one set of questionnaires will be included in all data sets. Subjects who fail to begin study therapy will be replaced.

10.2.3 Primary Endpoint

- Patient-reported financial toxicity will be assessed through the Functional Assessment of Chronic Illness Therapy (FACIT)-Cost questionnaire, administered at 1 month post-brachytherapy)
 - A preliminary estimate of the mean COST score in each arm will be reported for cohort 2, along with a 95% Gaussian confidence interval.

10.2.4 Secondary Endpoints:

- Quality-of-life will be assessed through to Evaluate responses to the QLQ30 Questionnaire and EN24 Questionnaire in the patient population.
 - The analysis of this data will be descriptive and tabular. No formal statistical testing will be done.
- Mean scores from FACIT-COST will be correlated with QLQ30 scores
 - Spearman correlation coefficients between FACIT-COST and QLQ30 summary scores will be reported for each arm. No statistical testing will be performed.

10.2.5 Exploratory Endpoints

The analysis of this data will be descriptive and tabular. No formal statistical testing will be done.

11 REGISTRATION GUIDELINES

Patients must meet all of the eligibility requirements listed in Section 4 prior to registration.

Study related screening procedures can only begin once the patient has signed a consent form. Patients must not begin protocol treatment prior to registration.

Treatment should start less than or equal to 10 business days after registration.

To register eligible patients on study, complete a Clinical Trials Office Patient Registration Form and submit to: [contact].

Treatment with experimental or control arms will be assigned at the time of enrollment. A randomization code will be created by a biostatistician and given to the Research Compliance Office to maintain and assign treatment to each patient as they are enrolled.

12 DATA REPORTING

12.1 Source documents and access to source data

Each participating site will maintain appropriate medical and research records for this trial, in compliance with ICH E6 and regulatory and institutional requirements for the protection of confidentiality of participants.

Source data are all information, original records of clinical findings, observations, or other activities in a clinical trial necessary for the reconstruction and evaluation of the trial. CRFs can be source documents as well as the medical record.

12.2 Quality assurance

QC procedures will be implemented beginning with the data entry system and data QC checks that will be run on the database will be generated. Any missing data or data anomalies will be communicated to the site(s) for clarification/resolution.

Following written SOPs, the monitors will verify that the clinical trial is conducted and data are generated, documented (recorded), and reported in compliance with the protocol, GCP, and the applicable regulatory requirements (e.g., Good Laboratory Practices (GLP), Good Manufacturing Practices (GMP)).

The investigational site will provide direct access to all trial related sites, source data/documents, and reports for the purpose of monitoring and auditing by HCI's RCO, and inspection by local and regulatory authorities.

12.3 Data collection and management responsibilities

Data collection is the responsibility of the clinical trial staff at the site under the supervision of the site PI. The investigator is responsible for ensuring the accuracy, completeness, legibility, and timeliness of the data reported.

All source documents should be completed in a neat, legible manner to ensure accurate interpretation of data. Black ink is required to ensure clarity of reproduced copies. When making changes or corrections, cross out the original entry with a single line, and initial and date the change. DO NOT ERASE THE ORIGINAL.

Copies of the electronic CRF (eCRF) will be provided for use as source documents and maintained for recording data for each participant enrolled in the study. Data reported in the eCRF derived from source documents should be consistent with the source documents or the discrepancies should be explained and captured in a progress note and maintained in the participant's official electronic study record.

Clinical data (including AEs, concomitant medications, and expected adverse reactions data) and clinical laboratory data will be entered into OnCore, a 21 CFR Part 11-compliant data capture system. The data system includes password protection and internal quality checks, such as automatic range checks, to identify data that appear inconsistent, incomplete, or inaccurate. Clinical data will be entered directly from the source documents.

12.4 Study records retention

Study documents should be retained for a minimum of 2 years after the last approval of a marketing application in an ICH region and until there are no pending or contemplated marketing applications in an ICH region or until at least 2 years have elapsed since the formal discontinuation of clinical development of the investigational product. These documents should be retained for a longer period, however, if required by local regulations. No records will be destroyed without the written consent of the PI, if applicable. It is the responsibility of the sponsor to inform the investigator when these documents no longer need to be retained.

12.5 Monitoring and Auditing

Clinical site monitoring is conducted to ensure that the rights and well-being of human subjects are protected, that the reported trial data are accurate, complete, and verifiable, and that the conduct of the trial is in compliance with the currently approved protocol/amendment(s), with GCP, and with applicable regulatory requirement(s).

Centralized monitoring will occur after the first 2, 5, and 10 patients are accrued and treated; then monitoring will occur throughout the trial until 30 days after the last patient has been treated twice yearly. Monitoring will be centralized, with random review of 25% of data, including data reporting and research sample acquisition.

Audits are performed independent of study monitoring. An initial audit will be conducted approximately one year after enrollment begins and annually thereafter. Audits may be conducted more frequently as requested by the Data and Safety Monitoring Committee (DSMC), RCO management, the Principal Investigator (PI), or Clinical Trials Office (CTO) depending on type and complexity of the trial, the level of risks to the trial subjects, and any identified problems or issues. Audit results will be reported to the HCI IRB as required.

Each clinical site will perform internal quality management of study conduct, data collection, documentation and completion.

